1.0 Abbreviations

MI	motivational interviewing
IRB	institutional review board
PPG	personal pain goal
FPG	functional pain goal
BQII	Barriers Questionnaire II
PSEQ	Pain Self-Efficacy Questionnaire
MISHCE	Motivational Interviewing Skills in Health Care Encounters
PEQ	Patient Experience Questionnaire
OET	Observed Engagement Table

Study Schema

[figure not shown]

Protocol Schema

2.0 Figure 1-Theoretical Framework

Cancer Pain Social Processes Theoretical Framework ([name] & Walker, 2018)

3.0 Objectives*

Purpose: To evaluate the acceptability and feasibility of using a cognitive behavioral intervention called motivational interviewing (MI) to help persons with pain from cancer set goals for managing their pain and improving pain control. Using MI, in our study the researcher will guide patients in goals-focused discussion of their cancer pain. At this time, there are no tested methods that clinicians can use for helping patients set these kinds of functional cancer pain goals (FPGs), despite the importance goal-setting in planning and managing healthcare behavior interventions. The study aims are:

Aim one: Evaluate the feasibility of motivational interviewing with regard to a) completion rate of a baseline and at least one follow-up study visit; b) the number of completed sessions; and c) patient acceptability of nurse-led motivational interviewing to set FPGs in the ambulatory palliative care setting.

Aim two: Explore relationships between patient-reported pain self-efficacy, attitudinal barriers to pain, and observed engagement in a motivational interviewing intervention focused on FPGs.

4.0 Background*

4.1 The Prevalence and Problem of Pain

Despite decades of research about cancer pain treatment, patients with advanced cancers have rates as high as 64% of moderate-to-severe pain (van den Beuken-van Everdingen, 2016).¹ In a 1998 seminal study, Turk et al. found that for persons with cancer pain, greater levels of anxiety were significantly correlated with lower levels of activity.² Although the fear of cancer pain is referenced in research papers making the case for improved pain control,^{3,4,5} only one study has measured its prevalence.⁶ LeMay et al. in a descriptive cross-sectional study measured fear of cancer pain prevalence and reported that patients with advanced cancers feared pain. Patient-reported fear of pain and pain severity were both significantly correlated with reduced self-reported functional capacity (B 0.19 p<.001, B 2.68 p<.001, respectively).⁶ Yet, it is unknown if fear contributes to worse pain, or if having had pain generates fear of pain. Attitudinal barriers patients reported, such as fear of addiction to opioids, also have been identified and positively correlated with pain severity ratings.^{7,8} An intervention which reduced patient barriers and increased patient feelings of power to control pain led to greater functional capacity.⁹ In a review of 74 longitudinal cancer pain intervention studies, Sauzet et al. reported the problematic finding that a lack of statistical outcomes reporting prevented definitive conclusions between interventions and sustained effects from being made.¹⁰ In our grounded theory study exploring social processes related to end-stage cancer pain management, when talking about times of good pain control respondents spoke of the importance of functional capacity by describing their activities.¹¹ We ascribed this activity talk to the social processes concept of ‘goals’, one of six fundamental pain management components. However, these participants who alluded to functional pain goals through indirect talk were not discussing or setting functional pain goals (FPGs) during routine pain management visits.¹¹ While goal-setting may seem like a logical step in a symptom management intervention, studies about goal-setting for managing pain have been limited to setting personal pain goals (PPGs), the numeric rating at which pain is considered tolerable,^{12,13} and have not resulted in significant patient-reported pain reductions¹³ or have not tested the effect of setting goals as an element of intervention.¹⁴ To date, there are no clear guidelines about how or when to assess cancer pain goals, and whether establishing patient-reported functional pain goals can contribute to reduction of moderate-to-severe pain. More research is needed to understand how patients’ FPGs can be assessed, discussed, and implemented in managing cancer pain.

4.2 Cancer Pain Interventions Gaps

Societal guidelines exist for cancer pain treatment, including acute, chronic, and breakthrough types,^{15,16} and researchers have identified barriers at the patient, caregiver, and clinician levels. Several systematic reviews of the literature on educational interventions for cancer pain self-management have concluded that across studies,

Testing Feasibility of Motivational Interviewing for Patient-Reported Cancer Pain Goals

generalizations about which types of interventions are effective cannot be made due to heterogeneity of interventions and mixed results reported within types of interventions delivered.^{17,18,19} For the most recent of these reviews, in 31% of the 26 randomized control trials (RCTs) included (dating from 1995 to 2017), authors reported significant differences in pain reduction for intervention and control groups in studies using combined video or written materials with in-person coaching.¹⁹ All but one of the included studies also measured and reported improved pain knowledge or barriers. However, because of the overall heterogeneity of interventions and outcomes measures, unclear reporting of study methods, and variations in intervention timing, the review authors were unable to make recommendations for effective cancer pain educational interventions.¹⁹ Another under-reported outcome in the review was testing of patient self-efficacy.¹⁹ Two cited studies reported on self-efficacy.^{18,20} Kravitz et al. studied general patient self-efficacy.²⁰ Koller et al. used a nurse coaching intervention to increase knowledge and reduce pain intensity with significant positive changes in pain knowledge but no significant reductions in patient reported pain intensity or increases in patient pain self-efficacy.¹⁸ In a literature review about motivational interviewing (MI), Jensen et al. reported that MI was effective for increasing self-care efficacy, and self-efficacy had been correlated with long-term pain coping, severity, and interference outcomes.²¹

Cancer pain can be acute, chronic, and breaking through at unexpected times, so early adaptive pain coping could be crucial for preventing pain crises and hospitalizations, as well as anxiety and distress over the course of the cancer illness trajectory. Vallerand et al. conducted an RCT of 317 African American patients with recent cancer pain ratings equal to or greater than 4/10, with 34% of the control group and 26% the intervention group having metastasized cancers.⁹ They reported that for participants in the Power Over Pain intervention group, perceived control over pain was significantly correlated with increased function ($p=0.121$) and decreased distress ($p=-0.09$).⁹ Wang et al. provided a telephone intervention to 137 patients with severe cancer pain (≥ 6 of 10) compared to 137 patients in a control group receiving usual care.²² While there were significant reductions in self-reported pain severity over the 12-month study period, the reductions were associated with patients who reported lower initial pain scores, were of higher socio-economic status, lower co-morbid burden, and concurrently reported reduced levels of depression.²² Vancleef & Peters studied relationships in 79 healthy volunteers who were randomly assigned to perceived pain control and self-efficacy groups and exposed to painful stimuli. They found significantly lower anticipated and actual pain intensity reporting in the high self-efficacy group, and nonsignificant but improved anticipated and actual pain intensity in the perceived control group.²³ Although the exact mechanisms which modulate self-efficacy and related symptoms have not been identified, interventions to increase patient self-efficacy in managing cancer pain have been studied.²³ Kelleher et al. reported that in a descriptive study of patient reported outcomes in cancer (n=178 breast and GI cancer patients), there were significant correlations between pain self-efficacy and intensity scores ($-.31$, $p<.001$) and pain self-efficacy and functioning ($-.29$, $p<.001$).²⁴

4.3 The Gap in Assessing and Managing Pain Clinically Using Cancer Pain Goals

Notable gaps in clinical practice research for cancer pain management exist for the processes of assessing and setting goals. Few studies have reported on use and testing of patient pain goals. Several recent studies assessed the feasibility of clinicians asking for and documenting use of personal pain goals (PPGs), where patients are asked to report a number between zero and ten at which their pain is tolerable. Fainsinger et al. conducted a descriptive longitudinal research study of 300 patients with cancer pain to compare stabilized-pain outcomes from PPGs with those from the Edmonton Classification System for Cancer Pain (ECS-CP) definition.¹² They found no significant differences in sensitivity and specificity of the two measures, except that for persons rating their initial pain as severe, the PPG, or patient reported goal, was more sensitive for detecting stabilized-pain later in the study than the ECS-CP.¹² No research studies have implemented this recent finding that points to the potential utility of this patient-reported outcome variable, the PPG. However, Zylla et al. conducted an institution-wide quality improvement initiative to determine feasibility and practice change in clinician assessment of PPGs.¹³ The investigators reviewed approximately 3,000 pain values from electronic health

Testing Feasibility of Motivational Interviewing for Patient-Reported Cancer Pain Goals

records each month over the 12-month program implementation period. Although there was a 71% increase (χ^2 $p < .001$) in clinician use of PPGs in conjunction with clinician and patient educational interventions, there were no decreases in reported pain for patients with moderate-to-severe rates (data not provided).¹³ Koller et al. included open-ended goal-setting in their RCT intervention study but did not test for statistical effects of this element of the intervention.¹⁴ Because cancer patients describe good pain days as those when they can function with as much normalcy as possible,¹¹ and functionality is associated with reduced anxiety,² less fear of pain,⁶ and feelings of empowerment,⁹ research which explicitly solicits FPGs from patients during clinical pain management encounters is warranted. Accordingly, our study will test feasibility of using MI as a nurse-led intervention for patient-reported cancer pain goal-setting.

4.4 Theoretical Framework and Preliminary Data

This study approaches the problem of cancer pain from a social processes theoretical framework illustrated in Figure 1,¹¹ as well as Prochaska and DiClemente's transtheoretical model of change that was developed for use in psychotherapy.²⁵ The cancer pain social processes theoretical framework identified behaviors and thought processes that were used by patients, family caregivers, and nurses in daily pain management in the home. These included pain goals, efficacy, perception, physical-emotional distance, communication, and agreement.¹¹ Social processes underpinned cancer pain management behaviors in complex ways. By viewing these processes in a context of multiple pain management collaborators (patients, caregivers, and nurses), clinicians and researchers can pinpoint areas of need. A lack of communication about personal and functional pain goals was evident between patients and caregivers, and patients and nurses in the participants of the grounded theory research study from which the framework was constructed.¹¹ In the study proposed here, we will specifically target setting of patient reported cancer pain goals by focused communication between a nurse and patient that uses motivational interviewing.

4.5 Motivational Interviewing to Set Patient-Reported Functional Pain Goals

MI is a cognitive behavioral approach that promotes coping by guiding patients to assess their circumstances and choose interventions specific to their needs and values. Working with patients to increase feelings of control is inherent to MI. MI has been used in both brief and extended clinical healthcare settings.²⁶ Two cancer pain studies have included MI as an element of a comprehensive intervention. Thomas et al. studied the effect of an MI-based telephone coaching intervention by a clinical nurse specialist as part of an RCT to help 318 patients manage their cancer-related pain.²⁷ Significant findings were increased function and improved mental and overall health in the intervention group, with no significant changes in pain intensity or attitudes over 12 weeks.²⁷ Coolbrandt et al. used MI as one component of an early overall symptom management intervention for 143 cancer patients beginning chemotherapy, randomized to intervention and control groups.²⁸ The interventions included use of MI and tailored nurse coaching in an initial inpatient session followed by a nurse phone session between two and four weeks later. They found that participants in the intervention group had significantly higher overall symptom self-efficacy scores at six weeks post-intervention than the control group (M 74, M 69, p.02 respectively).²⁸ To date, studies measuring the effect of MI on patient reported perceived control over cancer pain and pain self-efficacy have not been conducted. Nor have feasibility or patient acceptability of MI for cancer pain management been studied. However, feasibility studies have been conducted in other healthcare populations. For example, MI feasibility and fidelity were demonstrated in an RCT where trained community health workers delivered a brief culturally-tailored MI intervention to increase breast cancer screening rates for African American women visiting emergency departments.²⁹

Applying MI techniques for patients with cancer pain approaches the complex relationships underlying self-efficacy and perception of pain intensity, along with functional capacity by acknowledging the complicated nature of psychosocial and environmental issues. For example, we used constructivist grounded theory methods to generate the hospice caring triad cancer pain social processes framework, from which we identified social

Testing Feasibility of Motivational Interviewing for Patient-Reported Cancer Pain Goals
processes and their breakdowns in nursing pain management with patients and family caregivers.¹¹ Differences were reported in perception of pain control, communication about pain goals was lacking, and differences in physical-emotional distance occurred within groups of patients, caregivers, and nurses managing cancer pain at the end of life. Our theoretical framework (see Figure 1) provided an evidence-based outline of potential problem areas that researchers can use in developing interventions for improving pain outcomes when usual evidence-based practices do not seem to be effective in clinical contexts. The key problem identified in our study was the lack of communication with patients about any pain goals in developing plans for managing pain.¹¹

5.0 Inclusion and Exclusion Criteria*

5.1 Screening Procedures:

The PI or another member of the research team will view the ambulatory palliative care consult schedule weekly to identify eligible patient participants. The PI will then contact the scheduled provider to inform that the patient is eligible and to request permission to approach the patient in clinic after the scheduled consultation visit.

5.2 Sample Inclusion Criteria:

- At least 18-years of age
- Has an appointment with DFCI ambulatory palliative care service for cancer-related pain
- Can speak English

5.3 Exclusion Criteria:

- Diagnosis of delirium or other cognitive impairment

5.4 Special populations:

- None

6.0 Study-Wide Number of Subjects*

- We anticipate an overall study sample of 54 participants.

7.0 Study Timelines*

7.1 Participant duration in study:

Each participant will be enrolled in the study for the time it takes to return for their four scheduled intervention sessions, as long as those visits end by the time data collection closes, at the end of study month 10 (August 2019). The exact duration for each participant will be dependent on their clinic schedules with which the MI study intervention sessions will be aligned, as well as how many of the four MI intervention sessions individual participants complete. An example of brief participation is a participant who completes the initial session and returns for a second and final session one week later. An example of full participation is a participant who completes the initial session and returns for a total of four sessions prior to the study ending. Please see the study schema for a graphic depiction of the study timeline.

7.2 Estimated study completion time:

We anticipate that this research study will be ongoing for one year. Recruitment will occur over nine months. Data collection will begin at the time of recruitment and end when the last participant recruited in that period has completed up to four intervention sessions. Data analysis will take approximately two months. Complete analysis and processing of results is anticipated to conclude twelve months after the first day of recruitment.

8.0 Study Endpoints*

8.1 Data collection instruments:

To measure the study endpoints outlined in the specific aims, we will use the following instruments:

Intervention Feasibility (Aim 1)	Rate of participants completing at least two MI intervention sessions; study spreadsheet
Participant Total Intervention Usage (Aim1)	Rate of completed interventions out of four possible; study spreadsheet
Patient Intervention Acceptability (Aim 1)	Patient Experience Questionnaire (investigator-developed)
Attitudinal Barriers (Aim 2)	Barriers Questionnaire II (Ward & Gunnarsdottir, 2002)
Pain Self-Efficacy (Aim 2)	Pain Self-Efficacy Questionnaire (Nicholas, 1989)
MI Patient Engagement in Goals-Setting (Aim 2)	Observed Engagement Table (investigator-developed)
MI Fidelity	Motivational Interviewing Skills in Health Care Encounters (Petrova et al., 2015)

8.2 Measures:

8.21 Intervention feasibility (Aim one): Feasibility and total intervention usage rates will be calculated by extracting number of visits per participant from the research study registration spreadsheet. Intervention feasibility will be assessed by calculating the proportion of enrolled participants completing at least one follow-up MI session (at least two sessions total). The proportion of patients completing at least one follow-up intervention session will be estimated along with an exact 90% confidence interval. The MI intervention will be considered feasible if a 60% follow-up completion rate can be reached. With 54 participants, at least 26 (41%, 90% CI 36-60%) need to complete a follow-up interview to ensure that the upper bound of the exact 90% confidence interval contains 60%. Feasibility will be met for all participants completing at least two MI intervention sessions. The total intervention usage rate for each participant will be described by the number of interventions sessions attended divided by the total possible number of interventions sessions reported as the sample mean; the usage rate will be described (mean/std, median/range)..

Testing Feasibility of Motivational Interviewing for Patient-Reported Cancer Pain Goals

8.22 Participant intervention acceptability (Aim one): The Patient Experience Questionnaire (PEQ), developed by the investigator, will be used to summarize overall patient-reported acceptability in this study. Summary measures of median/range and mean/SD for total categorical PEQ scores, the time in weeks from the initial to follow-up intervention visit, and the number of completed intervention sessions will be reported.

8.23 Participant pain barriers (Aim two): Attitudinal barriers to pain management will be measured using the BQ-II which measures four attitudinal realms with 27 self-rated questions about pain beliefs. The BQ-II has been used in cancer pain studies with psychometrics demonstrating validity and reliability. For cancer patients, internal consistency of 0.89 (mean 1.52, SD 0.73) was reported and higher barriers were significantly correlated with increased age ($r=0.18$, $P=0.02$).³⁰ The total score for the BQ-II and PSEQ will be calculated at study entry and after the first follow-up visit and scores will be summarized (median/range, mean/SD). The paired difference in PSEQ and BQII will be estimated along with a 90% confidence interval. If additional sessions are completed, the scores for PSEQ and BQII will be plotted over time and trends will be explored with graphical methods. Spearman's correlation between the PSEQ and BQII will be estimated along with a 90% confidence interval at each measured time point.

8.24 Participant self-efficacy (Aim two): The study team will look at the correlation among the measures being explored, described herein: Pain self-efficacy will be measured using the PSEQ. In patients with a history of chronic pain and mean pain level rated at 6.2 out of 10, PSEQ demonstrated excellent internal consistency with an alpha of 0.92 and a test-retest reliability from baseline to three months of $r=0.73$, $P<0.001$.³¹ The total score for the BQ-II and PSEQ will be calculated at study entry and after the first follow-up visit and scores will be summarized (median/range, mean/SD). The paired difference in PSEQ and BQII will be estimated along with a 90% confidence interval. If additional sessions are completed, the scores for PSEQ and BQII will be plotted over time and trends will be explored with graphical methods. Spearman's correlation between the PSEQ and BQII will be estimated along with a 90% confidence interval at each measured time point.

8.25 Participant engagement in goal-setting (Aim two): Observed Engagement will be evaluated using the instrument developed by the investigator for this study in which behaviors indicative of active goal setting will be tabulated by the PI or RA. Observed engagement will be summarized categorically, and salient quotes will be extracted into the OET to give voice to participant experiences in study results dissemination.

8.25.1 The study team will look at the correlation among the measures being explored, specifically, pain barriers (BQII) and self-efficacy (PSEQ). The paired difference in BQII and PSEQ scores from sessions one and four will be estimated, along with a 90% confidence interval. If additional sessions are completed, the scores for BQII and PSEQ will be plotted over time and trends will be explored with graphical methods. Spearman's correlation between BQII and PSEQ will be estimated along with a 90% confidence interval at each measured time point.

8.26 MI intervention fidelity: Fidelity to MI methods will be assessed on 33% of interviews using the MISHCE which was developed specifically to measure fidelity in brief healthcare encounters. MISHCE evaluates the degree to which the person providing the MI session follows five domains key to MI. The domains are: 1) MI philosophy, 2) health interviewing, 3) motivation, 4) MI principles, and 5) interpersonal process. Each domain has specific behaviors that are rated as 1) deficient, 2) developing, 3) accomplished, or 4) N/A. MISHCE demonstrated acceptable internal consistency (0.75, CI 95%), good inter-rater reliability (15 of 22 intraclass correlation coefficients were excellent, 5 were good, 1 was fair and 1 was poor), and good-to-excellent test-retest reliability.³² Fidelity assessment will be conducted by the PI or RA.

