9.0 Procedures Involved*

Testing Feasibility of Motivational Interviewing for Patient-Reported Cancer Pain Goals

9.1 Study design:

This is a single-arm pilot study to assess feasibility and acceptability of a motivational interviewing intervention which will entail two-to-four intervention sessions per participant, participant completion of a battery of questionnaires specific to the intervention session, an investigator-led MI intervention at each session, and summary statistics (described below).

9.2 Study Procedures:

After written informed consent has been obtained and verbal consent confirmed participation in this study will involve between two and four intervention sessions.

9.21 Study Participation Compensation: Participants will be compensated with \$25 gift cards at the first and last visits (anticipated to be visits 1 and 4). Pending receipt of additional funding for participant compensation, participants may also be compensated at visits 2 and 3, if these are in addition to the first and last visits, and if this funding is granted to the research study.

9.22 Intervention Sessions: Each intervention session will include a battery of questionnaires, an MI intervention, and the investigator completing a goal(s) summary for the participant to take away. Participants may opt to complete Intervention Sessions 2, 3, and 4 in person on the DFCI campus or via telephone (or a mix). Session-specific content is outlined below. Session-specific content outlined below.

Testing Feasibility of Motivational Interviewing for Patient-Reported Cancer Pain Goals

Session 1:

Questionnaires:	Demographics survey* Pain location diagram (paper and pencil) BQ-II* PSEQ*
MI Intervention	Investigator-led discussion (described below)
Goals Summary	Completed by investigator
Gift Card (\$25)	Disbursed

* Paper and pencil form or tablet computer per participant preference.

Sessions 2 & 3:

Questionnaires:	BQ-II* PSEQ*
MI Intervention	Investigator-led discussion (described below)
Goals Summary	Completed by investigator
Gift Card (\$25)	None (Pending additional funding)

* Paper and pencil form or tablet computer per participant preference.

Session 4:

Questionnaires:	BQ-II* PSEQ* PEQ*
MI Intervention	Investigator-led discussion (described below)
Goals Summary	Completed by investigator
Gift Card (\$25)	Disbursed

* Paper and pencil form or tablet computer per participant preference.

Testing Feasibility of Motivational Interviewing for Patient-Reported Cancer Pain Goals

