17.0 Setting

Participant recruitment will take place in the ambulatory clinics where eligible patients are being seen for their scheduled palliative care consultations at DFCI. In-person study intervention visits will take place in private areas in the ambulatory clinics, consultation rooms, or meeting rooms on the DFCI campus. For participants who opt to have sessions 2, 3, or 4 via telephone, questionnaires will be given in person at session 1 or mailed to them in an unmarked envelope. The investigator will read the questionnaire aloud over the telephone as the participant reads their copy and the investigator will write their responses on the paper forms to be recorded in the Redcap database. Participant permission to audio record the intervention sessions will be obtained prior to beginning the motivational interviewing intervention each time. The intervention session(s) will be recorded via the telephone using the same recording equipment that is utilized for in-person intervention session interviews.

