32.0 Appendix E: Patient Experience Questionnaire

Patient Experience Questionnaire

Study ID # (to be filled out by study coordinator):

Instructions: For questions 1-6, please circle the answer that best describes your experience.

1) Were these sessions talking about pain helpful for you? YES NO NOT SURE

2) Were these sessions worth your time? YES NO NOT SURE

3) Would you recommend this type of pain session to others with pain from cancer? YES NO NOT SURE

4) Were you able to set a goal of something you hoped to achieve by having control of the pain? YES NO NOT SURE

5) Did you discuss your participation in these sessions, or parts of what we talked about, with your healthcare team? YES NO NOT SURE

6) Would you suggest also including caregivers these sessions? YES NO NOT SURE

For question 7, please write as much or as little as you would like to share.

7) Please let the research team know any other thoughts about your experiences with these sessions:

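### In the visible text the acceptability questionnaire (PEQ) is listed only at Session 4, so read literally it misses participants who finish earlier yet count as feasibility successes

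*Combined protocol and SAP*

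**What the plan says.** Patient acceptability is part (c) of Aim 1. The instrument list in 8.1 assigns it to the PEQ alone, and 8.22 confirms this: "The Patient Experience Questionnaire (PEQ), developed by the investigator, will be used to summarize overall patient-reported acceptability in this study". Section 8.22 plans medians, ranges, means and SDs of total PEQ scores, alongside weeks to the follow-up visit and number of completed sessions. It does not say when the form is given, who forms the denominator, or what happens when a form is missing.

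The session tables in 9.22 are the only readable schedule:
- **Session 1:** "Demographics survey* Pain location diagram (paper and pencil) BQ-II* PSEQ", with no PEQ.
- **Sessions 2 and 3:** BQ-II and PSEQ only.
- **Session 4:** BQ-II, PSEQ and PEQ.

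Participation need not reach Session 4. Section 9.2 states that "participation in this study will involve between two and four intervention sessions". Section 7.1 gives this case: "An example of brief participation is a participant who completes the initial session and returns for a second and final session one week later". Section 8.21 treats such a participant as a success: "Feasibility will be met for all participants completing at least two MI intervention sessions".

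**The concern.** A participant who stops after session 2 or 3 is a full success on the feasibility endpoint but, on the schedule as printed, is never asked whether the sessions were acceptable. The acceptability summary would then describe only those who came back three times. Willingness to return is plausibly related to how the sessions were received, so this group is selected on something close to the outcome. Ratings that were never collected cannot be recovered in the analysis.

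Early finishing need not mean dissatisfaction. Section 7.1 also names clinic schedules and the close of data collection as limits on the number of sessions. What is at stake is whether the reported acceptability can be called overall, as 8.22 calls it.

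**Working it through.** **1. The schedule set against the success rule.**

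| Last session attended | Foreseen in 7.1 or 9.2 | Feasibility success (8.21) | PEQ listed (9.22) |
|---|---|---|---|
| 1 | no | no | no |
| 2 | yes | yes | no |
| 3 | yes | yes | no |
| 4 | yes | yes | yes |

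The second and third rows are the gap.

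**2. The plan's own precision figure.** Sections 18.3 and 21.2 give at most ±11.9% for an exact 90% interval with 54 participants. The Clopper-Pearson interval is widest at 27/54, running from 38.1% to 61.9%, so half its width is (61.9 − 38.1)/2 = 11.9 points. The figure reproduces, but it concerns follow-up completion. The plan gives none for the PEQ.

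**3. How many would supply a PEQ.** From the documents: 54 participants and the 60% target. Assumed: exactly 60% reach session 2, and 60% to 80% of those present continue at each of the two later steps.
- At least two sessions: 54 × 0.60 = 32.4, about 32.
- Four sessions: 32.4 × 0.60² = 11.7, about 12; 32.4 × 0.80² = 20.7, about 21.
- Feasibility successes never asked: 32 − 12 = 20; 32 − 21 = 11.
- Responders as a share of the enrolled: 12/54 = 22%; 21/54 = 39%.
- Responders as a share of those with at least two sessions: 12/32 = 38%; 21/32 = 66%.

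**4. Precision.** By the method of step 2, the largest half-width for the proportion giving one answer to a PEQ item is 25.5 points with 12 responders, 19.3 with 21 and 15.6 with 32.

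**5. Illustration of selection.** Suppose 90% of four-session completers are favourable. The rate among all 32 is (completers × 0.90 + early stoppers × r)/32, where r is the assumed rate in early stoppers.

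| r | 12 completers, 20 early stoppers | 21 completers, 11 early stoppers |
|---|---|---|
| 60% | 22.8/32 = 71% | 25.5/32 = 80% |
| 70% | 24.8/32 = 78% | 26.6/32 = 83% |
| 80% | 26.8/32 = 84% | 27.7/32 = 87% |
| 90% | 28.8/32 = 90% | 28.8/32 = 90% |
| 100% | 30.8/32 = 96% | 29.9/32 = 93% |

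The observed 90% would be up to 19 points too high (90 − 71.25 = 18.75) in the first row, correct in the fourth, and 3 to 6 points too low in the last.

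**6. Bounds with no assumption about those never asked.** Counting all of them as unfavourable, then all as favourable:
- An observed 11/12 (92%) is compatible with 11/32 = 34% up to (11 + 20)/32 = 97%.
- An observed 19/21 (90%) is compatible with 19/32 = 59% up to (19 + 11)/32 = 94%.

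**The case against.** The best defence is that Session 4 stands for the last visit. Section 9.21 pays gift cards "at the first and last visits (anticipated to be visits 1 and 4"), and the gift card is itself a row of the same tables, shown as disbursed at Session 4 and, pending funding, not at Sessions 2 and 3. Read literally, someone whose last visit is session 2 would get no last-visit card, against 9.21. So in at least one row the Session 4 table does represent the anticipated last visit. Section 7.1 treats four sessions as the default. The PEQ looks back over several sessions ("Were these sessions talking about pain helpful for you"), as an end-of-participation form would. Section 8.22 reports number of sessions beside the scores, which would mean little if every responder had four. The study schema cited in 7.1 is a figure that could not be read here and may settle the timing.

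This makes the intent uncertain. It does not supply the instruction: 9.21 concerns compensation, and no readable passage extends the last-visit sense to the PEQ. A last-visit rule would also miss unplanned stops, since nobody knows at session 2 that a participant will not return.

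A reader might also infer that the study has no means of telling dissatisfaction from scheduling. That is too strong. Section 12.1 records a reason when a participant asks to be removed. It does not cover those who simply do not return, so the separation is partial.

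**Conclusion.** The point stands as a gap in the visible schedule: followed literally, Aim 1(c) is measured only in four-session completers. That the PEQ is listed nowhere else is certain for the text that could be read. That early finishers would in fact go unasked is less certain, because staff might apply the last-visit reading.

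Two stronger readings should be resisted. One is that acceptability will be overstated. Selection on adherence makes this plausible, but the documents fix neither size nor direction, and step 6 allows understatement too. The scenarios rest on assumed retention and assumed ratings, and on a favourable proportion that 8.22 does not plan, so they do not translate into the planned score summaries. The other is that the feasibility conclusion is compromised. It is not: the 60% criterion uses session counts only, and the acceptability summary is descriptive with no threshold.

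The change is worth making before data collection, because the loss cannot be repaired afterwards.

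**What to change.** Amend 8.22 and 9.22 as follows:
- Give the PEQ at each attended session from Session 2 on, or at minimum at Sessions 2 and 4.
- Use each participant's last available PEQ for the Aim 1 summary.
- Report responders out of those with at least two sessions and out of the 54 enrolled.
- Show results by number of sessions attended, with four-session completers as a secondary summary.

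This works whichever meaning of Session 4 was intended. Specifying the last attended session instead would be a smaller edit, but it depends on knowing in advance which session is last. The minimum version leaves a three-session participant with a rating from session 2 only.

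The cost is protocol wording and a seven-item form at sessions already held, a few minutes each time. Ratings will follow differing numbers of sessions, which the breakdown by sessions attended makes visible. Section 17.0 already covers telephone completion ("The investigator will read the questionnaire aloud over the telephone as the participant reads their copy"), but that means repeated, non-anonymous ratings given to the person who delivers the intervention, with a risk of courtesy answers that should be acknowledged in the report. Participants who attend only session 1 (54 − 32 = 22 under the assumption above) remain unmeasured. The enrolled denominator shows this but does not cure it.
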